#### 1.5.4 Clinical Studies

The clinical safety of ONC201 has been evaluated in a phase I clinical trial. The design was an open-label, dose-escalation phase I trial of mono-agent ONC201 in patients with advanced, refractory tumors who had exhausted or refused standard treatment options for their respective indications. The primary objective of this study was to determine the recommended phase II dose (RP2D) of ONC201 administered orally in

patients with advanced cancers, as well as to evaluate the safety and tolerability of the drug. Secondary objectives included pharmacokinetics and pharmacodynamics evaluation of ONC201 and preliminary assessment of anti-tumor efficacy.

An accelerated dose escalation design was employed to reduce the number of patients treated at potentially sub-therapeutic dose and to accelerate the determination of the recommended phase II dose. Ten evaluable patients (aged 47-80 years) received oral ONC201 once every 3 weeks at five dose levels ranging from 125 to 625 mg. The study design included only one patient per cohort until any patient experiences a grade 2 adverse event during the first cycle of treatment, defined as 21 days. Five dose levels (125 mg, 250 mg, 375 mg, 500 mg, 625 mg) were selected for the study. Enrollment at each subsequent dose level required that all patients enrolled at the prior dose level completed Cycle 1 dosing and were evaluated 21 days later to assess safety.

On average, patients received 3.1 doses of ONC201. Nine out of ten patients completed at least 2 cycles, 4 patients completed at least four cycles, and one patient received six cycles and remains on therapy. 625 mg was the highest dose administered and was determined to be the RP2D that surpassed the absorption saturation threshold by two dose levels. The only adverse event during the dose escalation phase that was possibly attributed to ONC201 was a low grade fever. No drug-related toxicities Grade >1 were observed in any patients in this study. Explorative laboratory studies and physical exams did not reveal any drug-related abnormalities. Similarly, cardiovascular assessments revealed no drug-related effects. Three Medwatch reports were filed with the FDA that reported events that were not attributed to the study drug.

### **1.6 Circulating Tumor Cells (CTCs) to assess TRAIL receptor expression**

CTCs will be isolated by a novel microfluidics CTC platform (VERSA Chip) that integrates CTC capture (>90% efficiency) with quantitative immunofluorescence and nucleic acid extraction/analysis[34-39]. CTCs will be captured using multiple antibodies (EpCAM, cell surface vimentin, MUC1, and CD133) determined by analysis of CTCs isolated in preclinical studies. Captured CTCs will be analyzed by quantitative immunofluorescence (TRAIL, TRAIL-R1 and TRAIL-R2) followed by RT-PCR analysis of mRNA levels of these targets using the VERSA Chip[37, 38].

CTCs will be drawn and analyzed if funding is secured.

### **1.7 Study rationale**

We hypothesize that ONC201 with an intermittent MR-diet will be effective in patients with metastatic TNBC. Expression of TRAIL receptor will be assessed in CTCs.

## **2. STUDY OBJECTIVES AND ENDPOINTS**

### **2.1 Primary Objective:**

2.1.1 To determine objective response rate (ORR) to ONC201 with a methionine-restricted diet in patients with metastatic TNBC.

### **2.2 Secondary Objectives:**

2.2.1 To determine progression-free survival (PFS) to ONC201 with a methionine-restricted diet in patients with metastatic TNBC.

2.2.2 To determine clinical benefit rate (complete and partial response plus stable disease) (CBR) at 4 months to ONC201 with a methionine-restricted diet in patients with metastatic TNBC.

2.2.3 To determine overall survival (OS) to ONC201 with a methionine-restricted diet in patients with metastatic TNBC.

2.2.4 To determine the safety of adding a methionine-restricted diet to ONC201 in patients with metastatic TNBC

2.2.4 To assess metabolic indices in patients with metastatic TNBC treated with ONC201 and a methionine-restricted diet.

2.2.5 To assess the expression of TRAIL receptor in CTCs prior, during and upon progression in patients with metastatic TNBC treated with ONC201 with a methionine-restricted diet.

**2.3 Exploratory Objective:**

2.3.1 To determine time to development of brain metastases or worsening of brain metastases in patients with metastatic TNBC treated with ONC201 with a methionine-restricted diet.

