**3. ELIGIBILITY CRITERIA**

**3.1 Inclusion criteria**

- \_\_\_\_ 3.1.1 Metastatic or unresectable TNBC (ER<10%, PR< 10% and HER2 negative either by IHC or in situ hybridization method by ASCO-CAP guidelines). For patients with a previous tumor sample with positive ER, PR and/or HER2 results, if the most recent biopsy meets study criteria, they will be eligible
- \_\_\_\_ 3.1.2 Measurable disease by RECIST 1.1. within 28 days prior to registration.
- \_\_\_\_ 3.1.3 Written informed consent and HIPAA authorization for release of personal health information. **NOTE:** HIPAA authorization may be included in the informed consent or obtained separately
- \_\_\_\_ 3.1.4 Females 18-74 years of age at the time of consent. Men are not eligible to participate.
- \_\_\_\_ 3.1.5 Any number of prior lines of systemic therapy for metastatic disease.
- \_\_\_\_ 3.1.6 ECOG PS of 0 or 1
- \_\_\_\_ 3.1.7 Prior cancer treatment, including radiotherapy, must be completed at least 14 days prior to registration and the subject must have recovered from all reversible acute toxic effects of the regimen to ≤ grade 1 or to baseline prior to initiation of that therapy. Grade 2 or higher exceptions include alopecia, up to grade 2 neuropathy or lymphopenia, and other grade 2 AEs or lab values not constituting a safety risk in the opinion of the treating physician. This criterion does not apply to lab tests outlined in criteria 3.1.10.
- \_\_\_\_ 3.1.8 No active CNS metastatic disease; subjects with prior definitive treatment of their CNS disease by surgical resection, SBRT or WBRT >28 days ago will be eligible if asymptomatic and off systemic steroids.
- \_\_\_\_ 3.1.9 Life expectancy of greater than 12 weeks.

- \_\_\_\_ 3.1.10 Normal organ and marrow function as defined per protocol definitions.
  - a. ANC  $\geq 1.5 \times 10^3/\mu\text{L}$
  - b. Platelet count  $\geq 100 \times 10^3/\mu\text{L}$
  - c. Hemoglobin  $\geq 9 \text{ g/dL}$
  - d. Total bilirubin  $\leq 1.5 \times \text{ULN}$
  - e. Transaminases AST/SGOT and ALT/SGPT  $\leq 2.5 \times \text{ULN}$ . If patient has liver metastases,  $\leq 5 \times \text{ULN}$ .
  - f. Creatinine  $\leq \text{ULN}$  (institutional normal)

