### **6.3 Protocol therapy discontinuation**

In addition to discontinuation from therapy related to toxicities as outlined in section 6.1, a subject will also be discontinued from protocol therapy and followed up per protocol under the following circumstances:

- Documented disease progression
- Discontinue methionine restricted diet for weight loss grade 2 or higher
- The treating physician thinks a change of therapy would be in the best interest of the subject
- The subject requests to discontinue protocol therapy, whether due to unacceptable toxicity or for other reasons
  - If a subject decides to prematurely discontinue protocol therapy ("refuses treatment"), the subject should be asked if he or she may still be

contacted for further scheduled study assessments. The outcome of that discussion should be documented in the medical records.

- A female subject becomes pregnant
- If protocol therapy is interrupted for >21 days.

Subjects will be removed from protocol therapy, and the site investigator notified, when any of the criteria listed above apply. The reason for discontinuation of protocol therapy will be documented on the eCRF in OnCore.

Subjects who discontinue protocol therapy will be followed every 3 months for 2 years after the end of treatment visit. Survival status and anti-cancer therapy (to include only first cancer directed therapy after study) will be collected from review of medical records or via telephone follow up.

If subjects discontinue study treatment prior to disease progression, scans during follow-up will be completed per standard of care, but RECIST measurements must be completed until disease progression or start of new anti-cancer therapy.

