- (2) Blood will be taken to assess plasma methionine levels at baseline, cycle 2 day 5, then day 5 of every other cycle, and at end of treatment. Subjects must be fasting. If necessary, these labs may be drawn as early as day 2, but prefer to be as close to day 5 as possible without going over.
- (3) If clinically indicated.
- (4) Optional biopsy prior to study entry.
- (5) Blood for circulating tumor cells will be taken at baseline, day 5 of cycle 2, and at end of treatment. If necessary, these labs may be drawn as early as day 2, but prefer to be as close to day 5 as possible without going over.
- (6) For women of childbearing potential. To be completed within 7 days of randomization. Must be repeated at cycle 1 day 1 if not completed in previous 7 days.
- (7) Subjects whose treatment is interrupted or permanently discontinued due to an adverse event (including lab values) should be followed per section 11.1.1.
- (8) Waist circumference, optional if not possible due to site limitations. Not required at screening.
- (9) CMP to include sodium, potassium, chloride, carbon dioxide, glucose, BUN, creatinine, calcium, albumin, total protein, alkaline phosphatase, aspartate aminotransferase (AST), alanine aminotransferase (ALT), and total bilirubin.
- (10) CT chest with or without contrast and CT with contrast or MRI of Abdomen/Pelvis to be completed during screening and  $\leq$  7 days prior to every third cycle starting at cycle four (approximately every 9 weeks; e.g. cycles 4, 7, 10, etc.). If subjects discontinue study treatment prior to disease progression, scans during follow-up will be completed per standard of care, but RECIST measurements must be completed until disease progression or start of new anti-cancer therapy.
- (11) Homocysteine/cysteine level at: baseline and every 3 cycles while on study (C1, C4, C7, etc.) and at end of treatment.
- (12) One block or 10 unstained slides.
- (13) labs/physical exam/ECOG PS does not need to be repeated if done within 7 days prior to C1D1

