### 13.7.3 Analysis plans for exploratory objectives

Kaplan-Meier methodology will be used to summarize time-to-event data, such as time to development of brain metastases or worsening of brain metastases in patients with metastatic TNBC treated with ONC-201 with a methionine-restricted diet. Graphical techniques (e.g., waterfall plots, KM curves, line plots) may be used when such methods are appropriate and informative.

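### The time-to-brain-metastasis endpoint has no mandatory baseline brain image and no scheduled brain imaging after screening, so it can only measure clinically detected CNS disease

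*Combined protocol and SAP*

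**What the plan says.** Section 2.3.1 gives one exploratory objective: "To determine time to development of brain metastases or worsening of brain metastases in patients with metastatic TNBC". Section 13.7.3 gives its analysis: "Kaplan-Meier methodology will be used to summarize time-to-event data, such as time to development of brain metastases or worsening of brain metastases". Nothing further is specified for this endpoint.

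In the Section 7 calendar the brain MRI row has a single mark, in the Screening column, qualified by footnote 3: "If clinically indicated". Footnote 10 sets the repeated imaging: "CT chest with or without contrast and CT with contrast or MRI of Abdomen/Pelvis to be completed during screening and" before every third cycle from cycle 4. The brain is not among the regions named. For subjects who stop treatment before they progress, the same footnote adds: "scans during follow-up will be completed per standard of care, but RECIST measurements must be completed until disease progression or start of new anti-cancer therapy".

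Section 6.3 describes what is collected after treatment, every 3 months for 2 years: "Survival status and anti-cancer therapy (to include only first cancer directed therapy after study) will be collected from review of medical records" or by telephone. CNS status is not listed.

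Subjects with earlier CNS disease can enrol. Criterion 3.1.8 reads "No active CNS metastatic disease; subjects with prior definitive treatment of their CNS disease by surgical resection, SBRT or WBRT" more than 28 days earlier are eligible if asymptomatic and off systemic steroids. The criterion does not say that a brain image is needed to show this.

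**The concern.** A time-to-event endpoint needs a known state at time zero and some rule for when the state is looked at again. Here the plan secures neither for all subjects. Someone without a clinical indication can start treatment with no brain image. If a lesion is found later, its date is the date of whatever scan found it, and nothing shows whether it was already there on cycle 1 day 1. Worsening needs an earlier image to compare with, and the plan does not require one even from subjects with treated CNS disease.

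At stake is what the reported curve means. Labelled as in Section 2.3.1, it would be taken as the time at which brain metastases appear or grow. Its event times would in fact depend on when each site had reason to scan. Analysis cannot repair this afterwards unless baseline imaging status, scan dates and reasons for scanning have been recorded.

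**Working it through.** The plan gives no event count, sample size or precision for this endpoint. The 34 subjects are set by ORR. There is thus no figure to reproduce, and the check is a comparison of the objective with the schedule.

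**Step 1. Imaging rows of the Section 7 calendar.**

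| Imaging | Screening | On treatment | End of treatment | Long-term follow-up |
|---|---|---|---|---|
| Chest, abdomen, pelvis | marked | marked, every third cycle from cycle 4 | blank | marked |
| Bone scan | if indicated | if indicated | blank | blank |
| Brain MRI | if indicated | blank | blank | blank |

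A cycle is 21 days, so the on-treatment body-imaging interval is 3 × 21 = 63 days, or 9 weeks. The number of scheduled brain assessments after screening is 0. The bone scan row carries the same footnote and keeps its on-treatment mark, so the blank brain cells look like the plan and not a table-reading fault.

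**Step 2. What the schedule yields for each kind of subject.**

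- *No brain image before cycle 1 day 1, lesion found later.* The recorded date is the scan date. The onset may lie anywhere before it, including before treatment. New and pre-existing lesions cannot be told apart.
- *Baseline image available.* New lesions and worsening can both be judged, but the date still depends on an unscheduled scan.
- *Treated CNS disease, no reference image.* Worsening cannot be judged.
- *Never imaged.* Absence of CNS disease is not confirmed by imaging. How such a subject enters the curve depends on a censoring rule that is not written.

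**Step 3. After treatment.** Contacts every 3 months for 2 years make 24 / 3 = 8 planned contacts. The items listed for them are survival and first subsequent therapy. The duty to complete RECIST measurements ends at progression or new therapy. A brain event that follows progression elsewhere therefore has no stated route into the database.

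**Step 4. Definitions.** Section 9.8.6 defines PFS and its censoring. Sections 9.8.3 and 9.8.7 define duration of response and OS. The brain endpoint has no event definition, no criterion for worsening, no censoring rule and no rule for death without a brain event. The last matters: Section 1.1 puts median survival in advanced TNBC at 13 months, so deaths within the follow-up period should be expected. If those deaths are censored, one minus the Kaplan-Meier estimate overstates the proportion who have a brain event.

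**The case against.** The strongest reply is that the endpoint is exploratory and descriptive, with no test or decision attached, and that leaving brain imaging to clinical judgement can be a deliberate economy. That stands, and it limits the priority of the point. It does not justify a label that promises more than the schedule can observe.

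Several stronger readings are tempting, and the documents do not support them.

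- *There is no baseline and no follow-up measurement at all.* Subjects with a clinical indication have a screening MRI, and those with treated CNS disease may well have one. Under Section 9.7 any new lesion is progression, so a brain lesion found on an unscheduled scan would be recorded. What is missing is a mandatory baseline and a schedule.
- *Every on-study brain scan is prompted by symptoms.* The footnote speaks of clinical indication, and on-study brain MRI is not addressed. Examination, history or local practice could also lead to a scan.
- *The plan counts never-imaged subjects as free of brain events.* Section 13.7.3 has no censoring rule, so it neither does this nor prevents it.
- *A given number of subjects will be misdated.* The documents give neither the prevalence of silent brain lesions at entry nor an expected event count.
- *The trial is set up to claim CNS control.* Section 1.5 lists crossing the blood-brain barrier among the drug's properties, but no CNS-efficacy hypothesis or success criterion is stated.

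**Conclusion.** The point holds in a limited form. Brain imaging is conditional at screening and unscheduled afterwards, so the planned curve would estimate time to clinically detected CNS disease. For subjects without a baseline image it cannot separate lesions present at entry from new ones and cannot show worsening. For subjects with one, only the timing is unscheduled.

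The supported measure of size is 0 scheduled brain assessments after screening, against body imaging about every 63 days on treatment. The number of subjects affected is unknown because the proportion who will have a baseline brain image is not given. The conclusion assumes that the calendar is complete as printed. The ORR test, its two-stage rule and the other planned analyses do not use this endpoint. The mismatch should be corrected, but it does not threaten the trial's main conclusion.

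**What to change.** No scan needs to be added.

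1. Restate Sections 2.3.1 and 13.7.3 (and the synopsis) as *time to first clinically detected CNS metastasis or CNS progression*, and say that asymptomatic CNS control is not assessed.
2. Record for each subject whether a brain image existed before cycle 1 day 1. Keep all subjects in the main summary and report events by baseline-imaging status. Label an event with no baseline image as *first detected on study, onset unknown*. Assess worsening only where a reference image exists. Counting events only in subjects with a baseline image would be a poor substitute, because it selects those scanned for a clinical reason.
3. Add a brain MRI mark, conditional on clinical indication, to the on-study and follow-up columns, as bone scan already has on study. Its purpose is to capture the date of, and reason for, images done in routine care. Report how many subjects were ever imaged.
4. Define worsening, censor at the last date on which CNS status was known, and treat death without a CNS event as a competing event, so that cumulative incidence is reported.

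The cost is wording in one objective and its analysis section, one calendar row and a few case report form fields. The claim becomes narrower, the subset for worsening will be small and selected, and follow-up will collect slightly more than Section 6.3 now lists.

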**3. ELIGIBILITY CRITERIA**

**3.1 Inclusion criteria**

- \_\_\_\_ 3.1.1 Metastatic or unresectable TNBC (ER<10%, PR< 10% and HER2 negative either by IHC or in situ hybridization method by ASCO-CAP guidelines). For patients with a previous tumor sample with positive ER, PR and/or HER2 results, if the most recent biopsy meets study criteria, they will be eligible
- \_\_\_\_ 3.1.2 Measurable disease by RECIST 1.1. within 28 days prior to registration.
- \_\_\_\_ 3.1.3 Written informed consent and HIPAA authorization for release of personal health information. **NOTE:** HIPAA authorization may be included in the informed consent or obtained separately
- \_\_\_\_ 3.1.4 Females 18-74 years of age at the time of consent. Men are not eligible to participate.
- \_\_\_\_ 3.1.5 Any number of prior lines of systemic therapy for metastatic disease.
- \_\_\_\_ 3.1.6 ECOG PS of 0 or 1
- \_\_\_\_ 3.1.7 Prior cancer treatment, including radiotherapy, must be completed at least 14 days prior to registration and the subject must have recovered from all reversible acute toxic effects of the regimen to ≤ grade 1 or to baseline prior to initiation of that therapy. Grade 2 or higher exceptions include alopecia, up to grade 2 neuropathy or lymphopenia, and other grade 2 AEs or lab values not constituting a safety risk in the opinion of the treating physician. This criterion does not apply to lab tests outlined in criteria 3.1.10.
- \_\_\_\_ 3.1.8 No active CNS metastatic disease; subjects with prior definitive treatment of their CNS disease by surgical resection, SBRT or WBRT >28 days ago will be eligible if asymptomatic and off systemic steroids.
- \_\_\_\_ 3.1.9 Life expectancy of greater than 12 weeks.

- \_\_\_\_ 3.1.10 Normal organ and marrow function as defined per protocol definitions.
  - a. ANC  $\geq 1.5 \times 10^3/\mu\text{L}$
  - b. Platelet count  $\geq 100 \times 10^3/\mu\text{L}$
  - c. Hemoglobin  $\geq 9 \text{ g/dL}$
  - d. Total bilirubin  $\leq 1.5 \times \text{ULN}$
  - e. Transaminases AST/SGOT and ALT/SGPT  $\leq 2.5 \times \text{ULN}$ . If patient has liver metastases,  $\leq 5 \times \text{ULN}$ .
  - f. Creatinine  $\leq \text{ULN}$  (institutional normal)
- \_\_\_\_ 3.1.11 Females of childbearing potential must have a negative serum pregnancy test within 7 days prior to registration. **NOTE:** Females are considered of child bearing potential unless they are surgically sterile (have undergone a hysterectomy, bilateral tubal ligation, or bilateral oophorectomy) or they are naturally postmenopausal for at least 12 consecutive months.
- \_\_\_\_ 3.1.12 Females of childbearing potential must be willing to abstain from heterosexual activity or must agree to use adequate contraception (hormonal or barrier method) for the duration of study participation and for 90 days after discontinuation of study treatment.
- \_\_\_\_ 3.1.13 Ability of the subject to understand and comply with study procedures for the entire length of the study.
- \_\_\_\_ 3.1.14 Able to swallow ONC201
- \_\_\_\_ 3.1.15 Be willing to discontinue vitamin and mineral supplements for the duration of the study if randomized to receive the methionine restricted diet.

### 3.2 Exclusion criteria

- \_\_\_\_ 3.2.1 No prior therapy with TRAIL receptor agonists
- \_\_\_\_ 3.2.2 Active infection requiring systemic therapy. Patients with a known history of HIV must have a CD4 count  $\geq$  the institutional lower limit of normal within 28 days prior to registration. Patients with HIV must also be on a stable anti-retroviral regimen for  $\geq 28$  days before registration.
- \_\_\_\_ 3.2.3 Pregnant or breastfeeding (**NOTE:** breast milk cannot be stored for future use while the mother is being treated on study).

- \_\_\_\_ 3.2.4 Known additional malignancy that is active and/or progressive requiring treatment; exceptions include basal cell or squamous cell skin cancer, in situ cervical or bladder cancer, or other cancer for which the subject has been disease-free for at least three years.
- \_\_\_\_ 3.2.5 Treatment with any investigational drug agent  $\leq$  14 days prior to registration or within 5 half-lives of that investigational product, whichever is longer.
- \_\_\_\_ 3.2.6 Subject who has had major surgery  $\leq$  14 days prior to registration or has not recovered from major side effects of the surgery (tumor biopsy is not considered as major surgery).
- \_\_\_\_ 3.2.7 Known hypersensitivity to any of the excipients of ONC201.
- \_\_\_\_ 3.2.8 Any impairment of gastrointestinal (GI) function or GI disease that may significantly alter the absorption of the study drugs (e.g., ulcerative diseases, uncontrolled nausea, vomiting, diarrhea, malabsorption syndrome, or small bowel resection).
- \_\_\_\_ 3.2.9 Any concurrent severe and/or uncontrolled medical condition that would, in the investigator's judgment, cause unacceptable safety risks, contraindicate subject participation in the clinical study or compromise compliance with the protocol (e.g. chronic pancreatitis, chronic active hepatitis, active untreated or uncontrolled fungal, bacterial or viral infections, etc.).
- \_\_\_\_ 3.2.10 Patients who follow a vegan or vegetarian diet

---

Investigator Signature

---

Date

---

Coordinator Signature

---

Date

